5.2 Exclusion Criteria

- 5.2.1 Patients who are currently receiving therapy (targeted, immune- or chemotherapy) without sign of progression.
- 5.2.2 Patients with squamous NSCLC.
- 5.2.3 Patients with more than 8 weeks between collection of tumor specimen and collection of blood sample for analysis. (Not applicable for patients progressing on EGFR targeted therapy with no biopsy at progression)

CONFIDENTIAL – PROPRIETARY PROPERTY OF GENOMIC HEALTH, INC.

Study Protocol

- 5.2.4 Patients changing EGFR therapy due to toxicity or preference without documented disease progression.
 - 5.2.5 Patients progressing on Osimertinib treatment.
 - 5.2.6 Patients with brain metastases only.
 - 5.2.7 Inability to comply with study and/or follow-up procedures.
 - 5.2.8 Unable or unwilling to provide written informed consent.
- 5.3 Study Duration and Withdrawal

Study participation for subjects ends after the research blood sample is drawn. There is no study-related follow-up with the participants but time to progression on therapy given after liquid biopsy or disease status at one year after liquid biopsy will be captured.

Subject participation is voluntary and can be discontinued at any time without loss of benefits or penalty. Should this occur, the reason for withdrawal must be documented in the original source document for the subject and written notification provided to Genomic Health. Participants are notified through the informed consent process that any de-identified research blood and tissue samples will be destroyed upon their request and not used for further analysis. If requested by the Investigator, a participant may be asked to discontinue the study if they are unable to meet the protocol defined study requirements.

Subjects that are screened but who are unable to undergo a successful blood draw or do not meet the protocol requirements will be considered screen failures.

6. STUDY OBJECTIVES

6.1 Primary Objective

Assess concordance of genomic alterations in *EGFR* (see appendix I) detected in plasma versus tumor tissue in stage IV non squamous NSCLC patients who are newly diagnosed or progressing on treatment.

6.2 Secondary Objectives

6.2.1 Assess concordance of genomic alterations in *ALK* (EML4-ALK fusions) detected in plasma versus tumor tissue.

6.2.2 Assess concordance of all detected alterations in plasma versus tumor tissue.

CONFIDENTIAL – PROPRIETARY PROPERTY OF GENOMIC HEALTH, INC.

Study Protocol

- 6.2.3 Assess concordance of mutation-specific NCCN guideline-based clinical actions based on alterations found in plasma versus tumor tissue and versus treatment received based on findings in tumor tissue.
 - 6.2.4 Assess concordance of detected genomic alterations separately in patients with newly diagnosed metastatic disease and patients progressing on treatment.
 - 6.2.5 Summarize the distribution of genomic alterations present in plasma, tumor tissue or both overall.
 - 6.2.6 Characterize the detection of *EGFR* T790M alterations in plasma in patients progressing on EGFR targeted therapy (erlotinib, gefitinib, afatinib).
- 6.3 Exploratory Objectives
- 6.3.1 Explore the association of genomic alterations detected in plasma or tumor tissue and time to progression, defined as first objective sign of progression by clinical examination or imaging, and response to therapy initiated after the liquid biopsy test.
- 6.4 Measures to Minimize Bias

Genomic Health staff involved in the processing of liquid biopsy samples will remain blinded to the central assessment of FPE tissue, Pathology and Clinical data collected during the study. The Genomic Health staff involved in the central assessment of FPE tissue will be blinded to the results of the liquid biopsy.

7. STUDY PROCEDURES

7.1 Subject Screening

Patients meeting the inclusion and exclusion criteria shall be offered enrollment in the study. Upon enrollment, a unique patient study identifier and unique specimen identifier(s) (for blood samples and tissue specimens), will be issued to each subject. The assigned identification numbers will not provide Genomic Health staff a direct link to private patient information.

7.2 Obtaining Informed Consent

Eligible patients may only be included in the study after providing written (witnessed, where required by law or regulation), IRB/EC approved informed consent. The Informed Consent Form will be reviewed and approved by the Sponsor or its designee prior to submission to the IRB/EC and initiation of enrollment. All appropriate

CONFIDENTIAL – PROPRIETARY PROPERTY OF GENOMIC HEALTH, INC.

Study Protocol

bills/legislative actions are to be considered and the Informed Consent Form amended, as appropriate. For example, the California Experimental Subject's Bill of Rights will be placed on the forefront of the Informed Consent Form for sites in California. The Informed Consent Form will be administered by the investigator or research staff authorized by the investigator using the most recent version of the informed consent document containing the IRB/EC stamp with dates of approval and or expiration (as required by applicable regulations and IRB/EC standard procedures). All research staff administering informed consent will be trained on Human Participant Protection prior to administering informed consent. Prior to participation in the study, the written Informed Consent Form will be signed and personally dated by the participant, and by the person who conducted the Informed Consent Form discussion. In order to ensure compliance with the HHS HIPAA Administrative Simplification Regulations, participants will be asked to sign a HIPAA authorization form or equivalent privacy law dictated authorization, where this is applicable. The signed HIPAA authorization forms, or equivalent, will allow researchers to use the participants' Protected Health Information in the research study.

7.3 Clinical Assessment and Data Capture

Demographic and clinical data on each participant will be collected at the enrollment visit. All clinical and demographic variables will be obtained from the clinical sites through a validated electronic data capture (EDC) system. The demographic variables will include age and gender. The clinical variables will include diagnosis, stage, histology of the tumor, marker status of primary tumor/metastatic site if available, site(s) of metastatic disease and treatment (prior targeted therapy, last therapy given prior to study enrollment and therapy after liquid biopsy). Additionally, dates of diagnosis, surgery, treatment, metastatic tissue biopsy, liquid biopsy, and of documented disease progression (defined as first objective evidence of progression (increasing tumor size or new lesions) by clinical examination or imaging) after liquid biopsy will be collected, when applicable. The clinical site will provide follow up clinical information including treatment given after liquid biopsy, best response to this treatment (complete response, partial response, stable disease or progressive disease) and date of progression or, at 12 months after liquid biopsy, if still on treatment without progression at that time. Follow up should also be completed upon patient death should that occur prior to first progression or 12 months after liquid biopsy. Genomic Health or its designee will provide the clinical sites with access to a validated EDC system for electronic case report form (eCRF) documentation. The eCRFs will be completed for each study participant through chart abstraction. It is the investigator's responsibility to ensure the accuracy, completeness, and timeliness of the data reported in the participant's eCRF. Source documentation and/or objective evidence supporting the eCRF data should indicate the participant's inclusion in the study and should document the dates and details of study procedures, adverse events, and participant status. The

CONFIDENTIAL – PROPRIETARY PROPERTY OF GENOMIC HEALTH, INC.

Study Protocol

investigator, or designated representative, should complete the relevant eCRF pages as soon as possible after information is collected, preferably on the same day that a study participant is seen for enrollment and blood draw. Any outstanding entries must be completed during data monitoring. An explanation should be given for all missing data. Individual subject files should be maintained in addition to the eCRFs. These files constitute "source data" and must be signed and dated by the study site research personnel who recorded the data (electronic signatures are acceptable for electronic medical records). All entries in the eCRFs must be supported by source data. The eCRFs must be kept up-to-date so that they reflect the latest observations on the subjects enrolled in the study. Each subject's file must include the original signed and dated Informed Consent Form and all specimen collection and shipping information.

This study will be registered with and posted on ClinicalTrials.gov (www.clinicaltrials.gov).

7.4 Collection, Shipment and Processing of Blood Samples

A total of 20 mL of venous blood will be collected in two Streck tubes (10 mL each) and shipped to Genomic Health the same day of collection. Blood collection should coincide, when possible, with routine clinical blood draws to minimize discomfort. A *Liquid Collection Form* (LCF) will be filled out, one per participant's blood collection, with the following information:

- Subject ID – unique identifier assigned to each subject, to remain the same number throughout all study collection events. This number will be linked to the clinical data.
- Collection Date and Time and additional administrative variables.
- All samples are to be shipped to Genomic Health on the day of collection via the courier specified for that site. Collections on Fridays may be sent out same day for delivery to Genomic Health on the following Monday, unless otherwise instructed by Genomic Health or its designee.

Genomic Health will perform blood pre-processing (plasma extraction) on the day of sample arrival. The blood samples received at Genomic Health will be handled and processed according to the liquid biopsy Specimen Preparation Instruction (SPI) manual and other Genomic Health related procedures. Genomic Health will notify the study site of all the samples received and their status as acceptable or rejected for further testing (i.e., quality or labeling issues) using the assigned de-identified study subject identifier. If the sample rejected or fails quality control metrics a second blood draw may be requested.

CONFIDENTIAL – PROPRIETARY PROPERTY OF GENOMIC HEALTH, INC.

Study Protocol

Any samples or remnant specimens (from blood) remaining after the conclusion of the study may be banked for future research. Future use will be explained in the ICF where the subject may elect to not approve banking their left over samples. All remaining samples or specimens will be de-identified and stored in an appropriate storage environment at Genomic Health. De-identified data associated with the banked left over samples will be stored in a secure Genomic Health database and will not be traceable to any identifiable protected health information.

7.5 Collection, and Processing of Pathology Samples

Enrolled subjects will have previously collected pathology tissue samples that will be utilized for the tissue-based sequencing if sufficient tumor material for analysis is available (as defined in section 4.1) and if patient approves of sending the material for analysis.

Local assessment of tumor tissue samples will be performed at each participating institution as per their clinical standard of care practices and results from the local assessment of genomic alteration status will be used. Each site will need to provide a single H&E slide to Genomic Health for an independent pathology review.

Genomic Health will receive and inspect the H&E slides according to approved internal receiving protocols. The received samples will be accessioned and quality inspected. Genomic Health standard histopathology assessments will be made from the single H&E slide of each FPE tumor tissue specimen by a Genomic Health designated pathologist(s) and will include: presence of tumor (adequate quantity).

Additional pathology measures will be obtained from the tissue biopsy pathology and mutation reports and entered into the electronic data capture system by the clinical site personnel.

Any residual DNA remaining after the conclusion of the study may be banked for future research. Tissue blocks or slides not used for analysis will be returned to the ordering physician but residual DNA will be stored by GHI. Future use will be explained in the ICF where the subject may elect to not approve banking their left over samples. All remaining samples or specimens will be de-identified and stored in an appropriate storage environment at Genomic Health. De-identified data associated with the banked left over samples will be stored in a secure Genomic Health database and will not be traceable to any identifiable protected health information.

CONFIDENTIAL – PROPRIETARY PROPERTY OF GENOMIC HEALTH, INC.

Study Protocol

8. STATISTICAL METHODS

8.1 General Methods

This section provides a general description of the statistical analysis methods. A detailed description of the analysis methods will be provided in the Statistical Analysis Plan, that will be developed blinded to any analytical test results (i.e. from the liquid biopsy tests and tumor tissue assessments) and finalized prior to the data lock for the interim analysis.

This is a descriptive study to characterize the concordance between the results of the Genomic Health LBMP based on plasma and genomic assessment of the tumor tissue. Both the liquid biopsy and the tumor tissue assessments will report the status of the investigated alterations in a binary manner as detected or not detected. No formal hypothesis testing is planned. Unless otherwise stated, two-sided 95% Clopper-Pearson confidence intervals will be reported²⁸.

The analysis of a single tumor biopsy cannot yield a reference standard for a liquid biopsy assessment due to tumor multifocality and intra- and inter-tumor heterogeneity in stage IV disease. As described in the FDA Statistical Guidance on Reporting Results from Studies Evaluating Diagnostic Tests (2007), when a new test is evaluated by comparison to a non-reference standard, it is not possible to directly calculate unbiased estimates of sensitivity and specificity. Therefore, due to lack of reference standard for analysis of liquid biopsies, it would not be appropriate to describe the comparative results of the study in terms of sensitivity and specificity. Instead, we will characterize the concordance in terms of positive percent agreement (PPA) and negative percent agreement (NPA) as presented in section 8.3, Table 4.

8.2 Analysis Populations

Statistical analyses will involve samples from patients with stage IV non squamous NSCLC. Samples that are not collected according to the sample preparation instructions, fail pathology review, fail to meet pre-specified analytical quality control metrics as defined by the Genomic Health LBMP's standard operating procedures, or fail to meet pre-specified quality control specification for the FPE assessment will be considered non-evaluable and will not be included in the analyses described in this section. Approximately 20% of enrolled patients are expected to have non-evaluable samples and thus results from approximately 248 evaluable patients are expected to be included in the analyses.

CONFIDENTIAL – PROPRIETARY PROPERTY OF GENOMIC HEALTH, INC.

Study Protocol

The primary analysis will be based on patients with non squamous NSCLC with evaluable plasma and tissue samples and reportable results from both the Genomic Health liquid biopsy test and tumor tissue assessments. The results of the central tissue assessments will be used when available. In patients without central CLIA laboratory results, local assessments of genomic alterations in tissue will be utilized. Exploratory analyses will include patients with evaluable samples from the Genomic Health liquid biopsy test and time to progression and available assessment of best response to therapy initiated after the liquid biopsy test.

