4.1 Required Procedures at Clinical Sites

Participants who are eligible and consent to participate in the study will provide a venous blood sample (2X 10 mL Streck tubes) at a single study related visit. Participants will have no further visits as part of this study. Participants data will be collected at time of progression or at 12 months after blood sample collection, whichever occurs first and in addition, data will be collected to permit outcome analysis of the interim analysis. Participation in the study will not alter clinical care. All other clinical procedures performed and collection of non-study data will be in accordance with each participating institution’s standard of care. Local assessment of tumor tissue samples will be performed at each participating institution as per their clinical standard of care practices and results from the local assessment of genomic alteration status will be used. Each site will need to provide a single H&E slide to Genomic Health for an independent pathology review.

CONFIDENTIAL – PROPRIETARY PROPERTY OF GENOMIC HEALTH, INC.

	<h2>Study Protocol</h2>
---	-------------------------

Table 3. Requirements by patient category to help identify correct patients and required materials at the single required patient visit. Detailed overview in Table 6 (page 39).

Requirements	Patient Category (see Figure 1)		
	A: Newly diagnosed with stage IV disease	A: Patient progressing on treatment (except if progressing on erlotinib, gefitinib, or afatinib)	B: Patient progressing on erlotinib, gefitinib, or afatinib
Biopsy/cytology/excision performed on primary or metastatic lesion	X		
Biopsy/cytology/excision performed on metastatic lesion		X	Only if available
Local pathology report	X	X	X (original diagnosis)
Local mutation report	X	X	X (original diagnosis)
Provide H&E slide from biopsy/cytology/excision to Genomic Health for independent review	X	X	X
Blood sample (2X 10 mL) collected in Streck tubes	X Prior to initiating new systemic anti-tumor treatment AND no more than 8 weeks after tissue biopsy	X Prior to initiating new systemic anti-tumor treatment AND no more than 8 weeks after tissue biopsy	X Prior to initiating new systemic anti-tumor treatment AND no more than 8 weeks after tissue biopsy only in cases where a biopsy was performed

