4.2 Processing of Samples and Data Management

The Genomic Health staff involved in the processing of liquid biopsy samples will remain blinded to the central assessment of FPE tissue, Pathology and Clinical data. The laboratory performing central assessment of FPE tissue will be blinded to the results of the liquid biopsy. The liquid biopsy, central FPE tissue assessment, Pathology and Clinical data will be independently processed and reviewed for quality. Once all data QC review and reconciliation are completed and data are locked, Genomic Health Data Management will merge the liquid biopsy, FPE tissue assessment, Pathology and Clinical data and prepare the SAS analysis dataset, following standard Genomic Health procedures. There will be only one, unique Specimen Identifier, and this number will not provide Genomic Health staff a direct link to private patient information. The direct link to private patient information is maintained and secured by study sites and Genomic Health will have no access to this information.

Please see section 8.6 for additional information regarding the planned Interim Analysis.

CONFIDENTIAL – PROPRIETARY PROPERTY OF GENOMIC HEALTH, INC.

Study Protocol

Sample specimens will not be used to develop genetic lines or nucleic acid banks. Archived samples and/or left over specimens may be used for quality control and/or for exploratory analysis of test result concordance specific to relevant cancer gene alterations that are not currently included in the Genomic Health mutation panel.

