5. STUDY POPULATION

Initially, 200 patients will be enrolled regardless of genomic alteration status in tumor tissue (First Enrollment Phase). This will be followed by a Second Enrollment Phase including approximately 39 patients with clinically relevant alterations in EGFR and 21 patients with alterations in ALK (EML4-ALK fusions) (as assessed in tumor tissue). In addition, 50 patients progressing on erlotinib, gefitinib, or afatinib will be included across the enrollment phases (see Table 2 and Figure 1).

Participants may be included in the study only if they meet all the criteria listed below in Section 5.1 and if they are not excluded by any of the criteria listed below in section 5.2.

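### Does section 8.2 give two conflicting rules for a patient whose central tissue assay fails quality control but who has a local result?

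*Combined protocol and SAP*

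**What the plan says.** Section 8.2 makes three relevant statements, in this order.

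1. Exclusion. Samples that "fail to meet pre-specified quality control specification for the FPE assessment will be considered non-evaluable and will not be included in the analyses" are left out, as are samples with collection faults, failed pathology review or failed plasma quality control. The section adds that "Approximately 20% of enrolled patients are expected to have non-evaluable samples", leaving about 248 patients.
2. Primary population. Patients are analysed "with evaluable plasma and tissue samples and reportable results from both the Genomic Health liquid biopsy test and tumor tissue assessments".
3. Choice of tissue result. Central results take priority when they exist. "In patients without central CLIA laboratory results, local assessments of genomic alterations in tissue will be utilized". The Synopsis (Sample Size) repeats this fallback without an exception for quality-control failure.

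Section 8.2 does not define the FPE assessment. Section 4.2 attaches the term to the central test: "The laboratory performing central assessment of FPE tissue will be blinded to the results of the liquid biopsy". Section 6.4 does the same.

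On who receives a central test, section 7.5 says tissue is sequenced "if sufficient tumor material for analysis is available (as defined in section 4.1", but section 4.1 holds no such definition. It says "Each site will need to provide a single H&E slide to Genomic Health for an independent pathology review", and Table 3 asks for that slide plus local pathology and mutation reports. Section 8.1 describes section 8 as general and refers detailed methods to the SAP, whose text is not in the document supplied.

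**The concern.** Take a patient whose tissue was tested centrally and failed quality control, but whose hospital reported a valid EGFR result. The exclusion appears to remove this patient. The fallback appears to keep the patient, because someone with a failed central assay has no central result. Nothing says which rule is applied first.

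Under the exclusion-first reading there is also an oddity. Two patients with equally poor tissue and equally valid local results are treated differently: the one never tested centrally stays in, and the one tested and failed drops out.

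The denominators of the primary positive and negative percent agreement (PPA and NPA) are at stake. The second enrolment phase takes "approximately 39 patients with clinically relevant alterations in EGFR", so a central failure there would decide whether a known tissue-positive patient counts. If such patients differ in plasma detection, the choice of rule could shift the estimate. If the choice were made after the interim results were seen, it could be influenced by them.

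**Working it through.** **Step 1: reproduce the plan's figures.** Evaluable patients = enrolled × (1 − 0.20).
- All patients (8.2): 310 × 0.80 = 248, as stated.
- Plasma and tissue (8.7): 260 × 0.80 = 208, as stated.
- Plasma only (8.7): 50 × 0.80 = 40, as stated.
- Table 5, 40/50 observed: exact 95% lower bound 0.663, against the stated 0.66.

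**Step 2: set the two rules side by side.**

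| | Exclusion | Fallback |
|---|---|---|
| Unit | sample | patient |
| Trigger | failed quality control for the FPE assessment | no central result |
| Consequence | sample not analysed | local result used |

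- *Read in order.* Evaluability is settled first, the primary population is limited to evaluable tissue, and central or local is then chosen within that set. The patient is out.
- *Read by unit.* The failed central sample is dropped, the patient has no central result, and the local one is used. The patient is in.
- *Third reading.* If the FPE assessment means whichever tissue assay supplies the result, the two rules never meet. Sections 4.2 and 6.4 make the central meaning more natural, but that is an inference.

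Each reading is coherent, and each yields a defined population and valid PPA and NPA. What is missing is the order of the rules.

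**Step 3: ceiling on the number affected.** Assign the whole 20% loss to central tissue failure with a valid local result.
- Concordance cohort: 260 × 0.20 = 52.
- EGFR-positive (PPA): 69 × 0.20 = 13.8, about 14; evaluable 69 × 0.80 = 55.2, about 55.
- First-phase patients without an EGFR alteration (NPA, Table 2): 10 + 160 = 170; 170 × 0.20 = 34.

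These cannot be realistic, because the same 20% also covers plasma, collection and pathology failures. The floor is zero. The documents do not split the loss by cause or say how many patients are tested centrally.

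**Step 4: effect on PPA.** Base: 44/55 = 80.0% (exact 95% CI 67.0% to 89.6%). Add k patients on local results, with plasma detection assumed between 50% and 80% (no source in the documents). Counts are rounded to whole patients.

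| k added | detection 50% | detection 80% |
|---|---|---|
| 3 | 46/58 = 79.3% | 46/58 = 79.3% |
| 7 | 48/62 = 77.4% | 50/62 = 80.6% |
| 14 (ceiling) | 51/69 = 73.9% (CI 61.9% to 83.7%) | 55/69 = 79.7% (CI 68.3% to 88.4%) |

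The largest shift, at an impossible ceiling and the lowest assumed detection, is 80.0 − 73.9 = 6.1 points. The base interval is 89.6 − 67.0 = 22.6 points wide.

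**Step 5: the planning benchmark in 8.7.** The chance of observing PPA of at least 75% at a true 80% is 80.3% with 55 patients (42 or more detected) and 86.0% with 65 (49 or more). Most of that difference comes from whole-number thresholds: 56 patients alone give 86.4%, because 42 detected is still enough. It says little about the rule.

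**The case for a change.** The strongest case for a change is that deferral to the SAP covers missing detail, whereas here the protocol already states two rules that a competent analyst could apply differently. The fallback is not limited to patients never tested centrally, and a failed assay is an obvious reason for having no central result. The central-laboratory subset in section 8.4 does not settle the matter, because these patients lie outside it under either rule. A one-sentence clarification would cost almost nothing, and section 8.6 allows interim results to go into an abstract.

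Much of this stands. Precedence is unstated, and analysts need to fix it before data are merged. But the plan already provides the safeguard against a choice driven by results: section 8.1 requires the SAP to be written without sight of plasma or tissue results and finalized before the interim data lock. The 8.4 subset is also identical under both rules, so one reported estimate does not depend on the choice.

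The argument that these patients would show different plasma detection is weak. Section 2 links lower sensitivity to low tumour burden and earlier stage, and a poor specimen is neither. The direction of any effect is unknown.

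The unmet cross-reference from 7.5 to 4.1, and the unqualified statements in sections 4, 4.1 and 7.5 that local results are used, are separate drafting slips. They do not establish a conflict in 8.2. If anything, they suggest that little tissue may go to central testing.

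**Conclusion.** The observation is accurate but is a matter of unstated precedence, not of contradictory rules. It is a gap that analysts fill sensibly in an SAP written blind to test results. Both readings give valid primary estimates, and section 8.1 plans no formal hypothesis test, so no decision turns on crossing a threshold such as 75%.

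The size cannot be taken from the documents. The affected group runs from zero to an unrealistic ceiling of 14 of 69 EGFR-positive patients. With 3 patients, expected movement in PPA is under one point; at the ceiling with 50% detection it is about six points, well inside the base confidence interval. The detection rates and the numbers added are assumptions, and so is the reading of the FPE assessment as the central assay. No change to the plan follows.
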